2.2 Study Design

This is a multi-cohort phase II trial of nelfinavir with hypofractionated radiotherapy and immunotherapy in advanced non-small cell lung carcinoma (NSCLC), melanoma, and renal carcinoma (RCC). The cohorts will be based upon histology (Melanoma vs NSCLC vs RCC) and prior immune checkpoint therapy (naïve vs refractory).

* See *Selection Pathway Section 3.1*

2.3 Endpoints

2.3.1 **Primary Endpoint:** Best objective Response (complete or partial, confirmed or unconfirmed) by irRECIST 1.1. Patients not known to have a response will be coded as non-responders.

2.3.2 **Secondary Endpoint:**

- Overall survival (OS): OS is defined as the duration of start of study treatment to death due to any cause. OS for patients last known to be alive will be censored at the date of last contact.
- Progression-free survival (PFS): PFS is defined as the duration from start of treatment to progression by RECIST 1.1, symptomatic deterioration, or death due to any cause. PFS for patients last known to be alive and progression-free will be censored at the date of last contact.
- Adverse Events by CTCAE 5.0
- Immune correlative studies including changes in T-cell repertoire

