6.8 Off Treatment Criteria

Patients will be removed from protocol therapy when any of the criteria listed in Section 6.3.8 applies. The source document will give the reason for ending protocol therapy and the date the patient was removed from treatment. All patients who discontinue treatment should comply with protocol specific follow-up procedures as outlined in Appendix 14.4. There are two exceptions to this requirement:

- Patient starts a new anti-cancer therapy and/or receives additional radiation treatment prior to follow-up procedures
- Patient withdraws consent for all study procedures or loses the ability to consent freely.

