6.9 Duration of Follow-Up

Patients will be followed after completion or removal from protocol treatment at two protocol-mandated time points. The first follow-up will occur 1 month after last dose of Nelfinavir (+/- 2 weeks), while the second follow-up will occur 6 months from date of enrollment (+/- 2 weeks). All patients who discontinue treatment should comply with the procedures below unless they meet the exceptions in Section 6.8:

- Physical Exam; ECOG
- Adverse Events Monitoring
- Concomitant Medication Monitoring
- Response Assessment by irRECIST 1.1
- Research Blood Collection
- Optional tumor biopsy

Survival follow-up will continue for 2 years from enrollment through office visits (scheduled at clinically indicated intervals, will vary by patient) and by review of medical record. Subjects may be contacted by phone call every 6 months to determine vital status.

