9.2 Method and Timing

Patients will undergo their initial response assessment by CT scans between weeks 12-14 after initiation of -PD1/PDL1 immune checkpoint inhibitor, every 12-14 weeks thereafter until progression, or as clinically indicated per institutional standards. The response assessments will not be read in real time. The formal reads of the response assessments will be completed once there is a statistically valid endpoints assessment at the end of trial accrual.

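### PFS is censored at last contact, which may be a vital-status call or chart check, so time without scans can count as progression-free and push the single-arm PFS curve upward

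*Combined protocol and SAP*

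**What the plan says.** All references are to the combined protocol and SAP.

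- **Event (2.3.2):** "PFS is defined as the duration from start of treatment to progression by RECIST 1.1, symptomatic deterioration, or death due to any cause". The first component needs imaging.
- **Censoring (2.3.2):** "PFS for patients last known to be alive and progression-free will be censored at the date of last contact". The OS rule uses the same date: "OS for patients last known to be alive will be censored at the date of last contact".
- **What a contact can be (6.9):** "Survival follow-up will continue for 2 years from enrollment through office visits", at intervals that vary by patient, "and by review of medical record". In addition, "Subjects may be contacted by phone call every 6 months to determine vital status". After treatment ends, only two visits with response assessment are mandated, the later one at 6 months from enrollment.
- **Who is released from follow-up procedures (6.8):** among the exceptions, "Patient starts a new anti-cancer therapy and/or receives additional radiation treatment prior to follow-up procedures".
- **Scans (9.2):** a first CT at weeks 12-14 of immunotherapy, then "every 12-14 weeks thereafter until progression, or as clinically indicated per institutional standards". Formal reads are made at the end of accrual, not in real time.
- **Analysis (11.2):** Kaplan-Meier medians and landmark percentages, with 6 months as the example landmark, and Cox models for PFS and OS. It adds no PFS censoring rule for missed scans or new therapy.

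**The concern.** Last contact suits OS, because a call establishes that the patient is alive. It does not establish that there is no RECIST progression. If imaging stops before progression and vital-status follow-up goes on to 2 years, the patient stays in the PFS risk set while the main type of event can no longer be recorded. The curve is then too high. Each cohort is a single arm of 20 patients, so no control arm shares the bias and a few patients can move the estimate. PFS by disease and prior-treatment cohort is a stated secondary objective, so these curves will be reported and read against outside results.

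**Working it through.** **Inputs.** The plan gives no expected PFS, event count or power for PFS, so it has no figure to reproduce. It also gives no share of patients who leave imaging before progression. All of the following are assumptions:

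- exponential progression (median 5 months) and exponential death (median 14 months), independent of each other;
- scans every 3 months, close to the 12-14 weeks in section 9.2;
- a share f leaves imaging, half after month 3 and half after month 6, regardless of prognosis;
- everyone is followed for vital status to 24 months, and in leavers only death is detected after the last scan.

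Under the written rule nobody is censored before month 24, so PFS just after a scan is a simple proportion.

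**Step 1: full imaging, 12 months.** 0.5^(12/5) × 0.5^(12/14) = 0.1895 × 0.5520 = 0.105.

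**Step 2: leavers under the written rule, 12 months.** They need to be progression-free at the last scan and alive at month 12.
- Last scan at month 3: 0.5^(3/5) × 0.5520 = 0.6598 × 0.5520 = 0.364.
- Last scan at month 6: 0.5^(6/5) × 0.5520 = 0.4353 × 0.5520 = 0.240.
- Mean: 0.302.

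**Step 3: whole cohort under the written rule, 12 months.**
- f = 20%: 0.8 × 0.105 + 0.2 × 0.302 = 0.144.
- f = 30%: 0.7 × 0.105 + 0.3 × 0.302 = 0.164.

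**Step 4: the same at 6 months.**
- Full imaging: 0.4353 × 0.5^(6/14) = 0.4353 × 0.7430 = 0.323.
- Leavers after month 3: 0.6598 × 0.7430 = 0.490. Leavers after month 6: 0.323. Mean: 0.407.
- f = 20%: 0.8 × 0.323 + 0.2 × 0.407 = 0.340.
- f = 30%: 0.7 × 0.323 + 0.3 × 0.407 = 0.348.

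**Step 5: other censoring rules, by simulation of the same set-up.** Ranges are across separate runs.

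| 12-month PFS | f = 20% | f = 30% |
|---|---|---|
| Written rule (last contact) | 14.2-14.6% | 16.0-16.4% |
| Survivors censored at last scan, all later deaths are events | 11.6-12.0% | 12.3-12.8% |
| Leavers censored at last scan even if they later die | 10.2-10.7% | 10.1-10.5% |
| Full imaging | 10.3-10.5% | 10.3-10.5% |

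At 6 months, the first two rules give 33.9% and 33.0% at f = 20%, and 34.9% and 33.7% at f = 30%. The difference is about 1 point. The median hardly moves (about 5.6 against 5.5 months).

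**Step 6: sensitivity to the assumptions.**
- If half of the leavers' unscanned progressions are found clinically 3 months later (assumed), the first two rules give 12.9% and 11.6% at 12 months for f = 20%.
- A second simulation used 13-weekly scans, a median of 10 months from progression to death, scans stopping after 0, 1 or 2 assessments, median PFS of 4 to 9 months and scan loss of 10% to 40%. The written rule exceeded full scanning by about 1 to 9 points at 6 months and 3 to 13 points at 12 months. The 6-month effect is larger here because imaging can stop earlier.
- In that second simulation, at median PFS 6 months and 20% loss, 12-month PFS was 25.0% with full scanning, 31.4% under the written rule and 25.3% with censoring at the last scan. It was 24.5% when deaths counted only within two scan intervals of the last scan. Over all settings this last rule fell at most 1.7 points below full scanning at 12 months.
- With no scan loss, all rules agree.

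**The case against.** The strongest case against has five parts.

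1. **Reading.** The rule covers patients last known to be both alive and progression-free, so last contact could mean the last contact at which both were known. This is a fair reading, but the text does not say it and the OS rule names the same date. The ambiguity itself needs one clarifying sentence.
2. **Who is exposed.** Section 9.2 plans scans until progression. The section 6.8 waiver concerns the Appendix 14.4 follow-up procedures and does not say that section 9.2 imaging stops. New therapy often follows progression, which is already an event. This stands: the exposed group may be small, and 20% to 30% is an assumption.
3. **Other detection.** Symptomatic deterioration is an event, and visits or chart review can reveal it or an outside scan. This stands and reduces the effect, as Step 6 shows. A patient clear at month 3 and credited with 24 months after a call is a worst case.
4. **Size against noise.** With 20 patients, the sampling SD at f = 20% was about 11 points at month 6 and 8 at month 12, larger than the shift. True, but sampling error averages out and this bias goes one way.
5. **Weight.** PFS is secondary, with no test, power or decision rule. This also stands.

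A reader might infer that moving the censoring date alone would bring 12-month PFS from 14-16% down to about 10%. The calculation does not support that. If deaths after imaging stops still count as events, the result is about 12%. Reaching about 10% requires a different rule, which also censors those later deaths at the last scan.

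**Conclusion.** The defect is real and moderate. Followed as written, section 2.3.2 can count time without scans as progression-free, and nothing in section 11.2 overrides it. The direction is upward in every scenario with scan loss. The size is not known from the documents. In the 5-month and 14-month scenario with 20% to 30% leaving imaging, the excess over full imaging is about 4 to 6 points at 12 months (14.4 - 10.5 = 3.9; 16.4 - 10.5 = 5.9) and about 2 to 3 points at 6 months (34.0 - 32.3 = 1.7; 34.8 - 32.3 = 2.5). These figures assume that leaving imaging is unrelated to prognosis and that progression is not found in any other way; clinical detection makes them smaller.

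The documents do not support a claim that PFS is grossly inflated, or that every late call will be counted as progression-free time. The response endpoint, which carries the only efficacy thresholds, is unaffected. The point is worth correcting before analysis but does not threaten the primary conclusion.

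**What to change.** Replace the censoring sentence for PFS in section 2.3.2 with:

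> PFS for patients without progression, symptomatic deterioration or death is censored at the date of the last disease assessment showing no progression (start of treatment if none). Patients who start new anti-cancer therapy before progression, or who die after two or more missed scheduled assessments, are censored at the last disease assessment before that.

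State whether additional radiation counts as new anti-cancer therapy here, since section 6.8 treats the two alike. Keep last contact for OS only. Report two sensitivity analyses: PFS censored at last contact, and PFS with all deaths counted as events.

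A missed scheduled assessment needs a single schedule. Section 9.2 gives 12-14 weeks and the Appendix 14.4 key gives 10-12 weeks, and these must be reconciled.

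**Cost.** About two sentences and a little more analysis work. Scan dates are already needed for response. PFS estimates become slightly less favourable, and the rule for deaths after missed scans can leave 12-month PFS slightly low (at most 1.7 points in the settings tried).

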3.0 STUDY AGENT INFORMATION

3.1 Immunotherapy Reference Therapy

PD1/PDL1 immune checkpoint inhibitor will delivered intravenously per standard of care.

Keytruda® (Pembrolizumab) FDA Approved Dosage and Administration

Metastatic Melanoma	200 mg intravenously over 30 minutes Every 3 weeks
Metastatic Non-Small Cell Lung Cancer	200 mg intravenously over 30 minutes Every 3 weeks

[figure not shown]
Opdivo® (Nivolumab) FDA Approved Dosage and Administration

Metastatic Melanoma	240 mg every 2 weeks or 480 mg every 4 weeks, intravenously over 30 minutes
Metastatic Non-Small Cell Lung Cancer	240 mg every 2 weeks or 480 mg every 4 weeks, intravenously over 30 minutes
Advanced Renal Cell Carcinoma	240 mg every 2 weeks or 480 mg every 4 weeks, intravenously over 30 minutes

Tecentriq® (Atezolizumab) FDA Approved Dosage and Administration

Metastatic Non-Small Cell Lung Cancer	1,200 mg intravenously over 60 minutes Every 3 weeks
---------------------------------------	---

Selection Pathway: In order of site preference

3.2 Receipt of Drug Supplies

Nelfinavir will be bought from commercial supply and stored as needed by Investigational Drug Services.

3.3 Dispensing of Study Drug

The drug will be dispensed by the UW and/or SCCA IDS.

3.4 Return or Destruction of Study Drug

At the completion of the study, there will be a final reconciliation of drug dispensed, drug consumed, and drug remaining. This reconciliation will be logged on the drug reconciliation form, signed and dated. Any discrepancies noted will be investigated, resolved, and documented prior to return or destruction of unused study drug. Drug destroyed on site will be documented in the study files.

4.0 SUBJECT ELIGIBILITY

4.1 Inclusion Criteria

4.1.1 Disease eligibility and Stage

- Histologically confirmed diagnosis of melanoma, NSCLC, or renal carcinoma.
- Previously treated or previously untreated stage IV melanoma, stage IV or recurrent lung cancer, and metastatic renal cancer by AJCC staging criteria
- Presence of a lesion that is suitable for hypofractionated radiotherapy

- 4.1.2 Disease measurement specifications
- 4.1.3 **Subjects must have measurable disease by RECIST criteria independent of the lesion to be irradiated.** Prior checkpoint inhibitor immunotherapy or chemotherapy is allowed as long as the last dose was received >14 days prior to enrollment.
- 4.1.4 Age ≥ 18
- 4.1.5 ECOG 0-2 (see Appendix 14.2)
- 4.1.6 Acceptable marrow function and hematologic indices for PD1/PDL1 immune checkpoint inhibitor and nelfinavir as per standard of care.
- 4.1.7 Ability to understand and the willingness to sign a written informed consent document.

4.2 Exclusion Criteria

- 4.2.1 Subjects who have had immunotherapy, chemotherapy, or radiation therapy within 14 days (6 weeks for nitrosoureas or mitomycin C) prior to entering the study or those who have not recovered from adverse events due to agents administered more than 4 weeks earlier.
- 4.2.2 Subjects may not be receiving other investigational agents.
- 4.2.3 Patients with untreated/active brain metastases as documented by CT or MRI within 2 months of study enrollment. By active brain metastases- we mean- actively symptomatic brain metastases requiring steroids.
- 4.2.4 Allergy or intolerance to nelfinavir or selected PD1/PDL1 immune checkpoint inhibitor.
- 4.2.5 Patients requiring steroids or other immunosuppressive therapy. Low-dose or topical steroids are allowable if being used as replacement therapy.
- 4.2.6 Patients receiving anti-retroviral therapy or other agents that are contra-indicated with nelfinavir due to drug-drug interactions.*
- 4.2.7 Pregnant or lactating patients.
- 4.2.8 Prior radiation that precludes delivery of hypofractionated radiotherapy.

* For a study regarding the safety and efficacy of high dose nelfinavir on patients with Kaposi's Sarcoma (KS), exclusion criteria included participants who were receiving any "strong inhibitors or inducers of cytochrome P450, family 3, subfamily A (CYP3A) or cytochrome P450, family 2, subfamily C, polypeptide 19 (2C19)"

Strong Inhibitors of CYP3A4:

- Antibiotics: clarithromycin, erythromycin, telithromycin, troleandomycin
- HIV: non-nucleoside reverse transcriptase inhibitors (delavirdine, nevirapine), protease inhibitors (ritonavir, indinavir, lopinavir/ritonavir, saquinavir), cobicistat-boosted antiretrovirals (e.g., elvitegravir); NOTE: Clinical trials have demonstrated that there are no clinically significant drug-drug interactions between nelfinavir and the following antiretrovirals:

efavirenz (strong CYP3A4 inhibitor), etravirine (strong CYP3A4 inhibitor); therefore, these antiretrovirals will not be excluded.

- Antifungals: itraconazole, ketoconazole, voriconazole, fluconazole, posaconazole
- Antidepressants: nefazodone
- Antidiuretic: conivaptan
- GI: cimetidine, aprepitant
- Hepatitis C: boceprevir, telaprevir
- Miscellaneous: seville oranges, grapefruit, or grapefruit juice and/or pomelos, star fruit, exotic citrus fruits, or grapefruit hybrids.

Strong Inducers of CYP3A4:

- Glucocorticoids: cortisone (> 50 mg), hydrocortisone (> 40 mg), prednisone (> 10 mg), methylprednisolone (> 8 mg), dexamethasone (> 1.5 mg)
- Anticonvulsants: phenytoin, carbamazepine, primidone, phenobarbital and other enzyme inducing anti-convulsant drugs (EIACD)
- Antibiotics: rifampin (rifampicin), rifabutin, rifapentine
- Miscellaneous: St. John's Wort, modafinil

Strong Inhibitors of CYP2C9:

- Antifungals: fluconazole; lists including medications and substances known or with the potential to interact with the CYP3A or 2C19

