11.3 Safety Monitoring

Toxicities will be monitoring on an on-going basis. If a Grade 5 adverse event with attribution as possibly, probably, or likely related to treatment is observed, then accrual to the study will be placed on hold with review by the DSMB needed. Consideration for the event will include if the patient was naïve to anti-PD-1/PD-L1 therapy or previously-exposed to anti-PD-1/PD-1 therapy.

A key toxicity of concern is hepatotoxicity, with grade 4 interpreted as a clinically significant event. Historical rates of Grade 3-4 hepatotoxicity with PD-1/PD-L1 therapy are 5-30% and 3% with nelfinavir. For monitoring of this event, evidence suggesting that the observed rate of Grade 4 hepatotoxicity exceed a true rate of 15% would result in temporary closure of the study with expedited DMSC review. Evidence to suggest this will be based on the lower bound of an 80% confidence interval excluding 15%, pooling all patients on trial (regardless of disease type and prior exposure to anti-PD-1/PD-L1) and assessed within enrollment cohorts. As such, accrual to the study will be placed on hold if 2/2-4, 3/5-8, 4/9-12, 5/13-17, 6/18-21, 7/22-26, 8/27-31, 9/32-36, 10/37-41, 11/42-46, 12/47-51, 13/52-57, 14/58-62, 15/63-67, 16/68-73, 17/74-78, 18/79-84, 19/85-89, 20/90-95, 21/96-100, 22/101-106, 23/107-111, 24/112-117, or 25/118-120 patients are observed to have a Grade 4 hepatotoxicity event.

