14.4 Treatment Calendar

	Baseline	Nelfinavir Only	Nelfinavir + 1st Dose Immunotherapy	Hypofractionated Radiotherapy	Hypofractionated Radiotherapy	Post Radiotherapy	Final Dose of Nelfinavir	Follow-up #1	Follow-up #2
Immunotherapy every 2-3 weeks until progression									
11-12 weeks of Nelfinavir									
Tests and Observations									
Physical Exam; ECOG	x		x	x	x	x	x	x	x
Adverse Events ^g		x	x	x	x	x	x	x	x
Drug Diary ^g		x	x	x	x	x	x	x	x
CT Scan ^g	x						x	x	x
iiRECIST 1.1 ^{a, g}	x						x	x	x
MRI Brain ^b	x								
Biopsy ^{c, g}						x	x	x	x
Laboratory									
CBC w/diff, Hgb, Platelets ^d	x	x	x	x	x	x			
CMP ^d	x								
Pregnancy Test ^e	x						x	x	x
Research Blood Collection ^{g, h}	x	x	x		x				
Treatment									
Nelfinavir ^j			x	x	x	x	x	x ^j	x ^j
Immunotherapy ^j				x	x	x	x	x ^j	x ^j
3 days x 6-8 Gy ^f				x	x	x	x	x ^j	x ^j

KEY

a. Baseline within 2 months of study entry. Repeat every 10-12 weeks or as clinically indicated

b. Within 2 months of study entry

c. Optional biopsy at end of service

d. Within 30 days of study entry

e. For WOCBP; Within 7 days of study entry

f. ACT simulation will be scheduled to plan for 3 fractions of 6-8gy each to a single lesion. Radiation will commence between 1st and 3rd dose of immunotherapy.

g. Research Procedure

h. 8 yellow top BD #364606 + 1 red top # BD 367820 ([name] specimen processing)

i. Pembrolizumab, Nivolumab, or Atezolizumab. Continue until progression.

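### Measured from the last dose, section 4.2.1 does not exclude unresolved toxicity from treatment given 15 to 28 days before entry, although it excludes the same toxicity from older treatment

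*Combined protocol and SAP*

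**What the plan says.** Section 4.2.1 has two limbs. The first excludes "Subjects who have had immunotherapy, chemotherapy, or radiation therapy within 14 days (6 weeks for nitrosoureas or mitomycin C) prior to entering the study". The second adds "or those who have not recovered from adverse events due to agents administered more than 4 weeks earlier".

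Section 4.1.3 restates the washout as an inclusion criterion, with no recovery condition: "Prior checkpoint inhibitor immunotherapy or chemotherapy is allowed as long as the last dose was received >14 days prior to enrollment".

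Three other criteria bear on patients with toxicity from earlier treatment:
- 4.1.6 requires "Acceptable marrow function and hematologic indices for PD1/PDL1 immune checkpoint inhibitor and nelfinavir as per standard of care". It gives no threshold and does not mention the liver.
- 4.2.4 excludes "Allergy or intolerance to nelfinavir or selected PD1/PDL1 immune checkpoint inhibitor".
- 4.2.5 excludes "Patients requiring steroids or other immunosuppressive therapy", with an allowance for low-dose or topical replacement steroids.

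For the blood count and the metabolic panel, the treatment calendar (14.4) sets the window in its key: "d. Within 30 days of study entry". It marks the blood count at several visits but the metabolic panel at baseline only.

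On the safety side, 7.2 records all adverse events from the start of nelfinavir. Section 11.3 places accrual on hold on a pooled count of Grade 4 hepatotoxicity, and 2.1.2 makes the rate of that event a secondary objective.

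**The concern.** A recovery clause normally applies to everyone who has passed the washout. Here it starts two weeks after the washout ends, so the rule runs backwards over that stretch: more recent unresolved toxicity is let through and older unresolved toxicity is not.

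This matters for the safety data. The Grade 5 rule in 11.3 asks whether the event is possibly, probably or likely related to treatment. The Grade 4 hepatotoxicity rule asks for no attribution; it counts observed events, whatever the disease or prior exposure. A liver abnormality brought into the study that worsens to Grade 4 after nelfinavir starts would count in full towards a hold, and again in the secondary safety objective, although part of its cause lies in earlier treatment. The calendar adds to the difficulty: if the only scheduled metabolic panel was drawn before the last prior dose, it cannot show toxicity from that dose, and nothing else scheduled would document that the problem was already present.

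**Working it through.** No power or error rate is involved. The check sets the time limits side by side.

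**Inputs.** Washout of 14 days, or 6 weeks (6 × 7 = 42 days) for nitrosoureas or mitomycin C (4.2.1). Last dose more than 14 days before enrolment (4.1.3), so day 15 is the earliest permitted. Recovery clause for agents given more than 4 weeks earlier (4.2.1), that is more than 4 × 7 = 28 days. Laboratory window of 30 days (14.4, key d).

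**Step 1: a patient with unresolved toxicity, by days from last dose to entry.**

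| Days since last dose | Washout limb | Recovery limb | Excluded by 4.2.1? |
|---|---|---|---|
| 0–14 | applies | does not apply | yes |
| 15–28 | does not apply | does not apply | no |
| 29 or more | does not apply | applies | yes |

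The uncovered stretch is 28 − 15 + 1 = 14 days. A patient 5 weeks (35 days) from the last dose is excluded; the same patient at 3 weeks (21 days) is not.

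**Step 2: nitrosoureas and mitomycin C.** The washout covers days 0–42 and the recovery limb covers day 29 onward. The limbs overlap, so there is no gap.

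**Step 3: do other criteria fill days 15–28?** 4.1.6 reaches hematologic toxicity only. 4.2.4 reaches toxicity that amounts to intolerance of nelfinavir or of the inhibitor chosen for the study. 4.2.5 reaches toxicity that still needs steroids or immunosuppression. Take non-hematologic toxicity from chemotherapy given 21 days earlier, not needing steroids: none of the three applies, and neither limb of 4.2.1 does.

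**Step 4: age of the qualifying metabolic panel.** Oldest permitted panel: day −30. Latest permitted prior dose: day −15. The panel can precede that dose by 30 − 15 = 15 days.

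**Step 5: weight of one carried-over Grade 4 event in 11.3.** The hold is triggered at 2 events among 2–4 patients, 3 among 5–8, and so on up to 25 among 118–120. One such event is 1/2 of the trigger at the start and 1/25 at the end. This shows when the rule is most sensitive, not how often such an event would occur.

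**The case against.** **The wording may reach further.** The recovery clause speaks of agents administered, whereas 4.1.3 speaks of the last dose. If any earlier administration counts, a patient on a 2-weekly inhibitor whose last dose was on day 15 had the previous one on day 15 + 14 = 29, and on a 3-weekly schedule on day 15 + 21 = 36. Both exceed 28 days, so the clause could apply. On that reading the gap shrinks to patients whose whole exposure to the agent falls within 28 days. The reading is possible and the text does not settle it. That is why the sponsor should say which is meant.

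**Other controls exist.** A reader might infer that a patient with unresolved Grade 3 inhibitor hepatitis at three weeks is simply eligible. The documents do not support that. Section 6.4 manages immune-related events above Grade 2 by withholding the inhibitor and giving steroids, so 4.2.5 would probably exclude many such patients, and 4.2.4 may exclude others. Cytopenia is partly covered by 4.1.6 and by the repeat blood counts. After entry there are 7 to 14 days of nelfinavir alone, and 6.3.6 and 6.3.8 restrict inhibitor dosing for related events. These points narrow the problem. They do not remove it: the rules in 6.3 act after entry, depend on attribution to the study agent, and do not affect what 11.3 counts.

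**The size is unknown.** Section 11.3 states "Historical rates of Grade 3-4 hepatotoxicity with PD-1/PD-L1 therapy are 5-30% and 3% with nelfinavir". Applied to the 60 refractory patients (3 cohorts of 20), this gives 0.05 × 60 = 3 to 0.30 × 60 = 18, and a reader might take that as the number at risk. It is not. The rate covers Grade 3 and 4 together, whereas the hold counts Grade 4 only, and it says nothing about how many events remain unresolved at days 15–28. Nor do the documents show that a few carried-over cases would close the study: only the earliest triggers are that low, and the consequence is a temporary closure with expedited review, where a pre-existing abnormality can be considered.

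**Conclusion.** The point holds as a gap in the eligibility wording. Measured from the last dose, 4.2.1 leaves days 15–28 without a recovery condition for all prior agents except nitrosoureas and mitomycin C, and the remaining criteria cover only part of that interval. The correct statement is that such a patient is not excluded by 4.2.1, which is weaker than being eligible. Separately, the qualifying metabolic panel may predate the last prior dose by up to 15 days.

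The route to harm is clear: Grade 4 liver events that originate before the study would enter an unattributed hold rule and a secondary objective. The frequency cannot be derived from the documents, and no figure for it should be quoted. The conclusion assumes that the recovery clause runs from the last dose. If it runs from any administration the gap is smaller, and the remaining fault is mainly ambiguity. On either reading the text should be amended, since the change is cheap and protects the safety data.

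**What to change.** Two changes to the text:

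1. Reconcile the two windows in 4.2.1, and 4.1.3 with them, so that no interval after the washout is left without the recovery condition. State whether the clause is measured from the last dose. The grade that counts as recovered, and any exceptions (for example endocrinopathy controlled on hormone replacement, with which 6.3.8 allows the inhibitor to be resumed), are for the sponsor's clinicians.
2. In key d of the treatment calendar (14.4), require the qualifying blood count and metabolic panel to be drawn after the last dose of prior systemic therapy as well as within the existing window.

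The cost is a short amendment in three places, later enrolment for some patients, and redrawn blood tests for some. Without stated exceptions, a wider recovery clause could also exclude patients with lasting but controlled toxicity, so the exceptions should be settled in the same amendment.
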